9.5 Study Schedule of Assessments

In the evening of each day the subject should rate their pain using the provided scale and record their rating in the eDiary. Refer to Table 1 Schedule of Assessments.

Table 1. Schedule of Assessments

Assessments	Screening/Baseline (Day 0)	Day 1 - 14	Research Extension (if applicable) Day 15 – 30
Inclusion/Exclusion Criteria	X		
Demographics	X		
Surgical Date	X		
Pain Assessment	X	X	X
Self-reported Pre-Existing Conditions*	X*		
OrthoCor Active System/SOC Intervention Use		X	X
Device Information	X		
OrthoPod Information	X	X	X
Concomitant Pain Medication Use	X	X	X
Adverse Event, related to the test device		X	X
Pregnancy test for WOCBP	X		

* Information to be collected if available

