9. BLINDING

The study is not blinded.

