11. GENERAL CONSIDERATIONS

11.1. General Methods

A repeated measures ANOVA will be utilized to assess statistical differences between the active and sham devices. A test of normality will be performed. If the data is not shown to be normally distributed, nonparametric methods may be used. All hypotheses are performed at an alpha equal to 0.05.

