12. STATISTICAL ANALYSIS

The data consists of multiple repeated measures and will be checked for normalcy and sphericity, and primary analysis will consist of ANOVAs for repeated measures and with other secondary analysis as appropriate for secondary hypotheses. Nonparametric methods will be used if the data is not normally distributed.

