12.1. Primary Endpoints

The primary endpoints of this study will be to compare the reduction of pain symptoms from baseline on the Mankoski Pain Scale after 2 weeks of treatment with the OrthoCor Active System device and Standard of Care.

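### The primary method hangs on an unspecified normality test with an unnamed nonparametric fallback, and SAP 11.1 and 12 disagree on whether the switch is mandatory

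*SAP*

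**What the plan says.** SAP 12 states that the data "will be checked for normalcy and sphericity, and primary analysis will consist of ANOVAs for repeated measures", and then: "Nonparametric methods will be used if the data is not normally distributed". SAP 11.1 covers the same ground in weaker terms: "A test of normality will be performed", and "If the data is not shown to be normally distributed, nonparametric methods may be used". It also sets the level: "All hypotheses are performed at an alpha equal to 0.05". Sidedness is not given.

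The primary endpoint in SAP 12.1 is to "compare the reduction of pain symptoms from baseline on the Mankoski Pain Scale after 2 weeks of treatment", device against standard of care. Ratings are daily (Protocol 9.5: "In the evening of each day the subject should rate their pain using the provided scale"), so each subject supplies a baseline value and up to 14 further values. SAP 9 states "The study is not blinded".

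Protocol section 11 names no statistical test, so it does not settle what the SAP leaves open. The documents name the Mankoski scale but give neither its range nor its step.

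**The concern.** A pre-specified primary analysis should let two statisticians with the same locked data reach the same primary p-value. Here they need not. One could test residuals, find no departure and report the ANOVA. Another could test the raw daily scores, reject, and move to a rank method of their own choosing. A third could reject and still keep the ANOVA under the optional wording of SAP 11.1.

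Each decision would be made with outcomes and arm labels available. At stake are the nominal 5% error rate and the credibility of the result. A reader of the report could not tell whether the method was chosen for its fit or for its answer.

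**Working it through.** **1. The two rules side by side.**

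| Item | SAP 11.1 | SAP 12 |
|---|---|---|
| Switch if non-normal | optional | mandatory |
| Normality test named | no | no |
| Quantity tested | not given | the data, described as repeated measures |
| Replacement method | not named | not named |

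The documents give no figure for the pre-test, so there is none to reproduce. The one planned figure at issue is the 0.05 level.

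**2. Does the trigger fire?** From the documents: up to 50 per arm (SAP 7), level 0.05, baseline plus 14 daily ratings. Assumed: normal underlying pain, rounded to whole numbers and clipped to 0–10. Single-day means were 2–5 with SD 1–2.5. Daily series had baseline means of about 4–6, with either subject-level random effects or serial correlation of 0.7. The table gives the share of simulated trials in which Shapiro-Wilk has p < 0.05.

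| Quantity tested | Rejection |
|---|---|
| All daily scores pooled | 100% |
| Raw single-day scores, both arms (100 values) | roughly 92–100% |
| Raw single-day scores, one arm (50 values) | 24–100% |
| Day-14 change, centred within arm | roughly 10–57% |
| Repeated-measures ANOVA residuals | roughly 5–58% |

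Residual rejection was 5–7% in the random-effect settings away from the floor and 38% when the mean fell from 4 to 1.5. It reached 58% with serial correlation and SD 2.5. The choice of test matters too. On single-day scores with mean 5, and on change scores, D'Agostino-Pearson rejected in 2–9% and Jarque-Bera in 0–5%. With mean 2, SD 2.5 and 100 values, they rejected in 93% and 85%.

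**3. Type I error.** There were 4,000 trials per setting, 50 per arm, no true difference and two-sided tests at 0.05. The three settings (baseline mean, change by Day 14, between-subject SD, within-subject SD) were (5.5, −1.5, 1.5, 1.3), (4, −2.5, 1.5, 1.3) and (5.5, −1.5, 2, 1.5). Each also had a random slope with SD 0.7.

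| Strategy | Type I error |
|---|---|
| One fixed method (t-test or Mann-Whitney, on Day-14 change or mean Day 1–14 change) | 4.4–5.2% |
| Fully specified switch: Shapiro-Wilk on arm-centred Day-14 change, then t-test or Mann-Whitney | 4.4–5.0% |
| Best of three rank tests: Day-14 change, mean change, Day-14 score | 11.8–12.4% |

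The Monte Carlo standard error at 12% is √(0.12 × 0.88 / 4000) = 0.005, about half a percentage point. Allowing for other settings, 11–13% is a fair summary. As a benchmark, three independent tests would give 1 − 0.95³ = 14.3%. The three analyses are correlated, so a value somewhat below that is expected.

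**4. Does switching gain anything?** With a true extra reduction of 1 point (baseline 5.5, SDs 1.5 and 1.3), power on Day-14 change was 68.1% for the t-test, 65.8% for Mann-Whitney and 66.9% for the specified switch. In that setting the pre-test buys no power.

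**The case against.** The strongest reply is that SAP 12 pairs normality with sphericity, so it can be read as an ordinary check of the ANOVA's assumptions. On that reading residuals are tested, and away from the floor they usually pass. Pre-testing as such does no measurable harm to type I error (4.4–5.0%). The 11–13% arises only if an analyst actually selects among fallbacks. SAP 12.1 also points to reduction from baseline after 2 weeks, which weighs against using the raw Day-14 score. With only two candidates, independence would give 1 − 0.95² = 9.75%, and correlation would bring it lower. Naming the test, the quantity and the fallback would close the gap without changing the primary method.

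Much of this stands: the pre-test is not itself the defect, and the inflation describes what the text permits, not what will happen. But the residual reading is only one of several. SAP 12 speaks of the data and never mentions residuals. SAP 5 describes the efficacy endpoint as a comparison of scores as well as a change from baseline, so the raw Day-14 score is not clearly excluded.

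A reader might infer that pain ratings will almost surely fail a normality test, so that the ANOVA is certain to be replaced. The documents do not support this. Scale range and step are not stated, the rates above run from about 5% to 100% according to what is tested, and SAP 11.1 does not oblige a switch. Nor can rejection be put down to rounding alone: at 0.1-point steps, raw Day-14 scores were still rejected in 5–99% of trials, with the high rates where scores pile up at the floor.

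A reader might also infer that a rank test would deprive the trial of an estimate to set against the non-inferiority margin. But the SAP specifies no Day-14 contrast or confidence interval for the ANOVA either, nothing bars an interval with a rank method, and the only margin (10%, SAP 7) is on proportions.

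**Conclusion.** The point holds in this form: the plan's own rule lets outcome data pick the primary analysis in an unblinded trial, through an unspecified test and an unnamed fallback, and two SAP sections conflict on whether the switch is required. The contradiction and the omissions are plain in the text and need no assumption.

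The size does rest on assumptions: whole-number 0–10 scores, 50 per arm, and the means and SDs listed. Under these, whether the ANOVA survives depends mainly on which quantity is tested and by which test. Free choice among three rank analyses takes type I error from the planned 5% to about 11–13%. The plan should be changed on this point before analysis. It does not show that any particular result would be wrong.

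**What to change.** In SAP 11.1 and 12, delete the normality test as a decision rule, together with both fallback sentences. State one primary analysis to be used whatever the distribution looks like: the baseline-adjusted between-arm difference at Day 14 with its 95% confidence interval, taken either as a contrast from the repeated-measures model or by ANCOVA, with robust standard errors. The SAP should pick one of these two. Baseline pain is already collected. Name one sensitivity analysis: a Wilcoxon rank-sum test on Day-14 change, with the Hodges-Lehmann shift and its confidence interval. Normality plots may stay as description.

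The cost is a short SAP edit and one more table. The sponsor gives up the option to switch, and the primary ANOVA is narrowed to a Day-14 contrast, which is a real change of primary model and should be declared as such. Fully specifying the switch instead would also hold the error rate, but the effect measure reported would still depend on a test result. Neither route resolves the separate mismatch with the 10% margin on proportions in SAP 7.

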12.1. Primary Endpoints

The primary endpoints of this study will be to compare the reduction of pain symptoms from baseline on the Mankoski Pain Scale after 2 weeks of treatment with the OrthoCor Active System device and Standard of Care.

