11.0 STATISTICAL ANALYSIS

The primary effectiveness endpoint of this study is the change from baseline of the OrthoCor Active System compared to the SOC intervention results after 14 days.

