11.1 Primary Endpoints

The primary objective is to compare the pain assessment scores of the SOC intervention to the OrthoCor Active System pain assessment scores after 14 days.

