10. STUDY ASSESSMENTS

Mankoski Pain Scale assessments are conducted during the study for a period of 2 weeks of treatment with OrthoCor Active system or Standard of Care. The enrolled participant will have a treatment period from Day 0 through Day 14 when the study ends, and a research extension period and assessments are conducted for a period of additional 2 weeks (see Table 1. Schedule of Assessments in protocol).

The primary endpoints as well as safety analyses will be evaluated at study end.

Exploratory analyses will be assessed after the extension period of additional 2 weeks.

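### The plan does not say which daily ratings make up the two-week pain score or which repeated-measures contrast is primary; a pre-specified Day 12-14 mean would settle both and probably reduce noise

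*SAP*

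**What the plan says.** **Endpoint.** SAP 12.1 will "compare the reduction of pain symptoms from baseline on the Mankoski Pain Scale after 2 weeks of treatment" with the device and with standard of care. Protocol 11.0 gives the "change from baseline of the OrthoCor Active System compared to the SOC intervention results after 14 days", and Protocol 11.1 sets out to "compare the pain assessment scores of the SOC intervention to the OrthoCor Active System pain assessment scores after 14 days". SAP 10 runs the treatment period from Day 0 to Day 14 and adds: "The primary endpoints as well as safety analyses will be evaluated at study end". None of these places names a particular evening or an averaging window.

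**Data.** Protocol 9.5 states: "In the evening of each day the subject should rate their pain using the provided scale and record their rating in the eDiary". Table 1 there shows one baseline assessment (Day 0) and assessments on Days 1 to 14, so each subject can supply 14 post-baseline ratings.

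**Analysis.** SAP 12 says: "The data consists of multiple repeated measures and will be checked for normalcy and sphericity". It then says that the "primary analysis will consist of ANOVAs for repeated measures". SAP 11.1 also names repeated-measures ANOVA. Neither section says which days enter the model, whether baseline is a covariate, or whether the primary test is the group main effect, the group-by-time interaction or a contrast at one day.

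**Missing data.** Protocol 11.3 prescribes a complete-case analysis. SAP 12.4 repeats this and adds that carrying the last visit forward will be considered. SAP 12.6 links complete cases to the per-protocol analysis and puts all subjects in the intent-to-treat analysis, without saying how gaps are filled.

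**The concern.** The endpoint is a statement about pain at two weeks, but the number that represents it for each subject is undefined. Three analyses fit the text and answer different questions:

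- A group main effect averages in Days 1 to 11, so it is not the effect after two weeks.
- A group-by-time test asks whether the two profiles differ in shape, not how far apart the arms are at the end.
- A Day-14 contrast matches the endpoint wording, but it rests mainly on one evening's rating and carries all of that day's noise.

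If Day 14 is meant, the neighbouring ratings already collected add little, and a missed Day-14 entry can remove the subject. If instead the ANOVA requires every day to be present, far more subjects can be lost.

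The trial is open label (SAP 9), and Protocol 9.4 foresees completing the study if significant improvement is seen after 32 subjects per group. Leaving the score and contrast open until arms have been compared would let the choice be guided by the results.

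**Working it through.** **Inputs.** The documents give no standard deviation, day-to-day correlation or daily completion rate for the pain score, so the plan has no figure of its own to reproduce here. The sample size in SAP 7 is built on a binary improved/not-improved response and does not enter this check. The following are assumptions:

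- any two late days correlate at *r*, varied from 0.6 to 0.9;
- each late day correlates at 0.5 with baseline;
- variance is equal across days and set to 1;
- the analysis is adjusted for baseline.

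**Step 1: residual variance.** For the mean of *k* late days it is (1 + (k − 1)r)/k − 0.5². For Day 14 alone (k = 1) this is 1 − 0.25 = 0.750. For Days 12-14 (k = 3):

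| r | (1 + 2r)/3 | minus 0.25 | ratio to 0.750 | cut |
|---|---|---|---|---|
| 0.6 | 0.733 | 0.483 | 0.644 | 36% |
| 0.7 | 0.800 | 0.550 | 0.733 | 27% |
| 0.8 | 0.867 | 0.617 | 0.822 | 18% |
| 0.85 | 0.900 | 0.650 | 0.867 | 13% |
| 0.9 | 0.933 | 0.683 | 0.911 | 9% |

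Other structures for a three-day mean give a similar picture. An unadjusted change score with baseline correlation 0.3 to 0.5 and r from 0.5 to 0.9 gives cuts of about 5% to 33%. A baseline-adjusted analysis under first-order autoregressive correlation (lag-1 0.7 to 0.95) gives about 9% to 25%.

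**Step 2: comparison with an average over all 14 days.** At r = 0.7 the residual variance is (1 + 13 × 0.7)/14 − 0.25 = 0.471, against 0.550 for the three-day mean. The three-day mean is thus about 17% more variable (0.550/0.471 = 1.17). It is not a precision gain over that contrast.

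**Step 3: dilution.** Suppose the treatment difference grows in proportion to the day number. The Day 12-14 mean then holds (12 + 13 + 14)/(3 × 14) = 13/14 = 93% of the Day-14 effect. Efficiency relative to Day 14 alone is (13/14)² = 0.862 divided by the variance ratio:

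- r = 0.7: 0.862/0.733 = 1.18
- r = 0.85: 0.862/0.867 = 0.99 (about break-even)
- r = 0.9: 0.862/0.911 = 0.95 (a loss of about 5%)

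Under the same growth, the all-14-day average holds only 7.5/14 = 54% of the Day-14 effect, which shows how far it is from a two-week estimate.

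**Step 4: missed entries.** Assume 90% daily completion, independent across days. Then 10% of subjects lack Day 14, and 0.1³ = 0.1% lack all of Days 12-14. If all 14 ratings were required, 0.9¹⁴ = 23% of subjects would be complete. The 0.1% is a best case, because a subject who leaves before Day 12 loses all three days.

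**The case against.** A reader might infer that the primary endpoint is the single Day-14 rating. No section says so. The SAP describes several ratings per subject, and a sphericity check has a purpose only with three or more time points, so the planned model uses more than one rating. What stands is that the time point and contrast are undefined, and that Day 14 is the most natural reading of the endpoint wording.

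A reader might also infer that averaging the last days is more precise than the planned analysis. That cannot be asserted, because the plan names no contrast, and Step 2 shows that a main effect over all 14 days could be more precise. That contrast, however, does not estimate the effect after two weeks.

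Nor is averaging free. It moves the target slightly earlier, and Step 3 shows that the gain can disappear. Protocol 4.2 reports a pilot in which the reduction appeared within 3 days and persisted to day 42. This suggests an early plateau and little dilution, but it comes from knee osteoarthritis only and is a within-cohort comparison. Protocol 15.2 has the device arriving in 3 to 5 days. If days count from enrollment, Days 12-14 fall earlier in actual device use, but that affects Day 14 alone as well.

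On missing entries, carry-forward could rescue a missed Day 14. It is only to be considered, it is worded for visits although Protocol 9.0 describes a single on-site visit, and Protocol 11.3 does not mention it.

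**Conclusion.** The point holds as a gap in specification with an inexpensive improvement attached. The documents do not say which ratings form the two-week score or which contrast is primary, and the planned model does not settle it.

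Relative to Day 14 alone, a Day 12-14 mean lowers residual variance by about 36% to 9% for assumed late-day correlations of 0.6 to 0.9 and an assumed baseline correlation of 0.5. It also makes the score less dependent on a single diary entry. The size rests entirely on those assumptions. The benefit is clearest if the treatment difference has levelled off by Day 12. With linear growth it is lost at a correlation of about 0.85 and slightly reversed at 0.9. The change is advisable; the trial does not fail without it.

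**What to change.** In Protocol 11 and SAP 12.1:

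1. Define the two-week score as the mean of the available ratings on Days 12, 13 and 14, with at least one required.
2. Compare change from baseline to that score between arms, with the baseline rating as covariate, and name this as the primary contrast.
3. Keep Day 14 alone as a sensitivity analysis, which would show any dilution.
4. Fix this wording before any between-arm comparison, including the one implied by Protocol 9.4.

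The cost is a change of wording in the two documents; no extra data are collected. The downside is slight dilution if the effect is still growing between Days 12 and 14.

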12.2. Exploratory Endpoints

The exploratory endpoints of this study will be to compare the reduction of pain symptoms from baseline on the Mankoski Pain Scale after 4 weeks of treatment with the OrthoCor Active System device and Standard of Care.

Usage (device records use), feedback via participant diaries, usability assessment, user preferences will be summarized as descriptive statistics.

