	
improvement in outcomes, but there is value in restorative therapies to help maintain functionality.
 
The Orthocor Active System delivers OrthoCor's patented Pulsed Electromagnetic Field (PEMF) therapy, a noninvasive, temporary relief for pain. The key to OrthoCor's therapy is the use of specialized PEMF technology. In particular, PEMF works at the source of injuries, and helps accelerate the body's natural anti-inflammatory and recovery responses. Inside every Active System is the OrthoCor, a microchip that delivers PEMF directly to the source of injuries. Furthermore, PEMF has been shown to stimulate reaction pathways that result in pain and inflammation reduction.

Study Assessment/ Evaluation:	Pain assessments will be conducted utilizing the Mankoski Pain Scale which will be compared to the pain assessments of subjects who were prescribed the Standard of Care (SOC) intervention.
Study Endpoints:	
Primary Safety Endpoint: The safety endpoint of this study will be the adverse events reported with the OrthoCor Active System pain after 2 weeks of use.
 
Primary Efficacy Endpoint: The efficacy endpoint of this study will be the comparison of the OrthoCor Active System pain assessment scores to the Standard of Care (SOC) intervention after 2 weeks of use.

Exploratory Assessment:	
Exploratory Assessment: The exploratory assessment of this study will be the performance of the OrthoCor Active System after an additional 2 weeks of use and is intended for research and publication only.

Number of Patients:	
Up to 100 subjects will be enrolled in order to achieve up to 50 using the OrthoCor Active System and up to 50 using the Standard of Care (SOC) intervention. The patients will be enrolled consecutively at the participant site until enrollment is met.
 
For the exploratory assessments, the 50 subjects who received SOC will have the opportunity to cross-over and use the OrthoCor Active system.

Number of Sites:	Five (5) sites are anticipated
Anticipated Study Duration:	3-5 months
Study Eligibility Criteria	
Inclusion Criteria:
 
Participants must meet ALL of the following:
 
 1. Individuals presenting with pain in superficial soft tissue, such as ankle, back, knee, wrist, elbow, shoulder, foot, or neck pain,

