8.3 Subject Population

The target population for this measurement consists of both males and females, presenting to the designated study sites with pain in superficial soft tissue, such as in the ankle, back, knee, wrist, elbow, shoulder, foot, or neck who are prescribed the use of the OrthoCor Active System or Standard of Care (SOC) intervention.

Eligible subjects must meet the inclusion and exclusion criteria described in Sections 8.4 and 8.5. Any questions from the investigative site regarding a potential subject's eligibility for enrollment must be discussed with the Sponsor (or designee) prior to consenting and enrolling the subject into the study for the investigational measurement.

It is estimated that up to 100 subjects may be enrolled into the study.

Patients will be enrolled consecutively at each participant site until up to 50 using the OrthoCor Active System and up to 50 using the Standard of Care (SOC) intervention have enrolled. The CRO will stratify the arms (OrthoCor Active System vs SOC) by selecting the arm alternatively. The patients will be enrolled consecutively at the participant site until enrollment is met.

As part of exploratory research extension, patients using the OrthoCor Active system will have the opportunity to continue on the trial for an additional 2 weeks. Participants assigned SOC have the opportunity to cross-over using the OrthoCor Active system for the additional 2 weeks. Participation in the exploratory extension is optional.

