4. STUDY DESIGN

This is a prospective, multi-center, randomized, open label study that will enroll up to 100 subjects. Subjects will consist of both males and females, presenting to the designated study sites with pain in superficial soft tissue, such as in the ankle, back, knee, wrist, elbow, shoulder, foot, or neck who are prescribed the use of the OrthoCor Active System or Standard of Care (SOC) intervention.

Patients will be enrolled consecutively at each participant site until up to 50 using the OrthoCor Active System and up to 50 using the Standard of Care (SOC) intervention have enrolled. The CRO will stratify the arms (OrthoCor Active System vs SOC) by selecting the arm alternatively. The patients will be enrolled consecutively at the participant site until enrollment is met.

As part of exploratory research extension, patients using the OrthoCor Active system will have the opportunity to continue the trial for an additional 2 weeks. Participants assigned SOC will have the opportunity to cross-over using the OrthoCor Active system for the additional 2 weeks. Participation in the exploratory extension is optional.

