5. STUDY OBJECTIVES AND ENDPOINTS

The primary safety and efficacy objectives are:

Safety endpoint of this study will be the adverse events reported with the OrthoCor Active System after 2 weeks of use.

Efficacy endpoint of this study will be the comparison of the OrthoCor Active System pain assessment scores to the Standard of Care (SOC) intervention after 2 weeks of use. The primary effectiveness endpoint of this study is the change from baseline of the OrthoCor Active System compared to the SOC intervention.

The exploratory objectives, for publication only, are comparison of the performance of the OrthoCor Active System to standard of care after additional 2 weeks of use.

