7. SAMPLE SIZE

The sample size estimates are calculated assuming a binomially distributed response of improvement or no improvement. Without any a priori estimates, the most conservative estimate (widest interval) is using a baseline for the standard of care (SOC) of 50% improvement. The null hypothesis for a non-inferiority study is that the experimental treatment is inferior to the standard of care. The alternative hypothesis is that the experimental treatment is non-inferior to the standard of care.

The sample size per group is based on the comparison of two proportions with baseline proportion of 50% for the experimental treatment assuming a 50% response for SOC and a non-inferiority margin of 10% assuming 90% power. The assumed confidence is 95% or a type 1 error rate of 5%.

The study will enroll 100 subjects, up to 50 using the OrthoCor Active System and up to 50 using the Standard of Care (SOC) intervention. The patients will be enrolled consecutively at the participant site until enrollment is met. The CRO will stratify the arms (OrthoCor Active System vs SOC) by selecting the arm alternatively.

For the exploratory assessments, the 50 subjects who received SOC will have the opportunity to cross-over and use the OrthoCor Active system.

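### SAP 12.2 gives SOC subjects who cross over neither an analysis group nor a baseline of their own, so their 4-week change from Day 0 mixes SOC-phase and device-phase change

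*SAP*

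**What the plan says.** SAP 12.2 sets the exploratory endpoint, which is to "compare the reduction of pain symptoms from baseline on the Mankoski Pain Scale after 4 weeks of treatment with the OrthoCor Active System device"; the same sentence goes on to name Standard of Care beside the device. It therefore names two groups and a 4-week horizon for both. SAP 5 words the objective differently, as a "comparison of the performance of the OrthoCor Active System to standard of care after additional 2 weeks of use". The protocol synopsis names only the device: "the performance of the OrthoCor Active System after an additional 2 weeks of use".

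The only column marked as a baseline in Table 1 (Protocol 9.5) carries the words "Screening/Baseline (Day 0". Neither document defines a second baseline at the start of the extension.

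On crossover, SAP 4 states: "Participants assigned SOC will have the opportunity to cross-over using the OrthoCor Active system for the additional 2 weeks". Protocol 8.3 says the same, and both make the extension optional. SAP 7 ties the crossover to this endpoint: "For the exploratory assessments, the 50 subjects who received SOC will have the opportunity to cross-over and use the OrthoCor Active system".

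Two further passages affect timing. Protocol 9.4 provides that, if the study is declared complete early, remaining SOC subjects may go onto the device without having reached the extension. Protocol 15.2 gives 3 to 5 days for a device to arrive.

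**The concern.** A 4-week change from Day 0 describes one treatment only if the subject stayed on that treatment for 4 weeks. A subject allocated to the device who continues meets that condition. A SOC subject who crosses over does not, and the formula in SAP 12.2 then returns a sum over two treatments under a label that fits neither.

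Up to 50 of the 100 subjects could be in this position. Pain of this kind may ease over two weeks through natural recovery, regression to the mean or response to SOC. If so, a published 4-week figure could attribute that easing to the device. It could equally attribute device-phase change to SOC, depending on a classification that the analyst would have to choose without guidance from the plan.

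**Working it through.** The documents attach no figure to this endpoint, so there is nothing to reproduce. The check is an identity, followed by illustrations on assumed values.

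**Inputs from the documents**
- Reference point: Day 0 (Protocol Table 1).
- Horizon: 4 weeks (SAP 12.2).
- SOC phase: 14 days, then an optional 2 weeks on the device (Protocol 8.3 and 9.0; SAP 4).
- Group sizes: up to 50 per arm.
- Ratings: every evening in the eDiary (Protocol 9.5), so a score just before the switch is already collected.

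**Inputs not in the documents (assumed)**
- a, the fall in pain during the SOC phase: 0.5 to 2 points.
- b, the fall during the device phase: 1 point.
- m, the number of crossover subjects: 10, 25 or 50.

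**Step 1: one crossover subject.** The change from Day 0 is

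(Day 0 − end) = (Day 0 − last SOC rating) + (last SOC rating − end) = a + b.

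Example: Day 0 = 6, Day 14 = 4, end of extension = 3. The change from Day 0 is 6 − 3 = 3. Of this, 6 − 4 = 2 arose on SOC and 4 − 3 = 1 on the device.

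With b = 1:
- a = 0.5 gives 1.5
- a = 1 gives 2
- a = 2 gives 3

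With b = 0, the change from Day 0 is still 0.5 to 2 points.

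**Step 2: three possible classifications.**
1. *Counted as device.* All of a enters the device result.
2. *Counted as allocated (SOC).* Nothing enters the device result, but b enters the SOC result. With a = 1 and b = 1, half of the 2-point SOC figure arose on the device. The distortion of the comparison is b minus what a further 2 weeks of SOC would have produced, which is not observed.
3. *Excluded for lacking 4 weeks on either treatment.* There is no mixture, but the data that SAP 7 links to the exploratory assessments go unused.

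SAP 11.2 does not settle the choice. It defines its populations by enrolment, treatment received and data completeness, and it does not mention crossover.

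**Step 3: effect on a group mean under classification 1.** Suppose 50 device subjects continue and m crossover subjects are pooled with them. Relative to using b alone for the crossover subjects, the device mean shifts by m × a / (50 + m).

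| m | a = 1 | a = 2 |
|---|---|---|
| 10 | 10/60 = 0.17 | 20/60 = 0.33 |
| 25 | 25/75 = 0.33 | 50/75 = 0.67 |
| 50 | 50/100 = 0.50 | 100/100 = 1.00 |

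**Step 4: the comparator.** Subjects who decline the extension stop at Day 14. SOC subjects who enter it are offered the device. No text describes a subject who stays on SOC to 4 weeks, so the SOC side of SAP 12.2 has no described source of data.

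**The case against.** A reader might infer that the plan counts crossover subjects as device subjects, so that the device result is always inflated by the SOC-phase improvement. The documents do not support that. SAP 12.2 is worded as a two-group comparison, and no passage places crossover subjects in the device group for this endpoint. Protocol 9.4 does speak of SOC subjects moving to the active group, but that concerns access to the device, not analysis. If subjects are analysed as allocated, the misattribution runs the other way. If pain rises during SOC, the sign changes under the device classification too. Nor does the protocol synopsis fix a Day 14 reference: it speaks of performance after the extra 2 weeks, which names a time point and not an interval of change.

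It can also be said that a SOC group at 4 weeks is not ruled out. Crossover is an opportunity, and Table 1 marks a combined device/SOC use row for the extension. But no text describes continued SOC, and any such group would be self-selected. SAP 12.4 mentions carrying the last visit forward, but a Day 14 SOC score carried forward is a 2-week result under a 4-week label.

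Finally, the endpoint is exploratory, and the 2-week primary endpoint is untouched for subjects who complete 14 days on SOC. This limits the severity. It does not remove the defect: either classification that uses the crossover data against Day 0 yields a mixed-treatment quantity, and excluding those subjects is nowhere stated.

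**Conclusion.** The point holds in this form: SAP 12.2 leaves the group and the baseline of crossover subjects undefined. Their change from the only defined baseline combines SOC-phase and device-phase change, and the 4-week SOC comparator has no described group behind it. The identity in step 1 needs no assumption beyond a switch from SOC to device.

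Size and direction are conditional. They depend on the classification chosen, the number who cross over and the SOC-phase change, none of which the documents give. Under the device classification with assumed SOC-phase falls of 1 to 2 points, the device mean moves by 0.17 to 1.00 points as crossover subjects go from 10 to 50, with all 50 device subjects continuing. Under the as-allocated classification, the device mean does not move and the SOC mean absorbs the device-phase change. The plan should be corrected because the extension results are intended for publication, although the primary analysis does not depend on it.

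**What to change.** In SAP 12.2:

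- Report crossover subjects separately from the original device arm, whose 4-week change stays measured from Day 0.
- Define the crossover baseline as the last rating before first device use, whenever that occurs. Do not fix it at Day 14: Protocol 9.4 allows an earlier switch, and the delivery time in Protocol 15.2 can push first use later.
- Define the crossover endpoint as the change from that baseline after 2 weeks of device use.
- Label the result an uncontrolled within-subject change, since recovery over time is still part of it.
- Remove the wording that implies a 4-week comparison of device with SOC, and bring the objective in SAP 5 into line.

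The cost is a few sentences. The daily eDiary already supplies the ratings; the date of first device use must be identifiable for each crossover subject. The downside is that the reported crossover change may look smaller and the 4-week comparative statement is lost.
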